### Statistical research

- 1) statistical data processing
- 2) comparison and analysis of initial data

After data acquisition, statistical analysis will be performed using SPSS Statistics version 22. For quantitative data, the nonparametric Mann-Whitney U test and parametric t-test will be performed, and for qualitative studies, the nonparametric Fisher's exact test and the parametric  $\chi^2$  test will be performed. Also, logistic regression for categorical outcomes and survival analyzes (non-parametric Kaplan-Meyer and parametric Cox regression) will be performed.

**Age:** 18 years and older

**Gender:** All

**Inclusion of healthy volunteers:** Not

| Groups  | Inclusion criteria   | Exclusion criteria  |
|--|---|--|
| Patients on an extracorporeal life support system with heart failure                             | 
 
• Implantation of intravenous ECMO
 
• Hemodynamic support with vasopressors and / or tonics;
 
• Procalcitonin level <math>\geq 1</math> ng / ml;
 
• Invasive hemodynamic monitoring;
 
• Written informed consent.
 
   | 
 
• Age less than 18 years old
 
• Terminal hepatic or renal failure just before the procedure
 
• Patient's written refusal to participate in the study
 
 |
| Patients on an extracorporeal life support system with pulmonary failure                         | 
 
• IV ECMO implantation
 
• High levels of venous and arterial CO2 (CO2 > 50 mmHg),
 
• Low paO2, SvO2, SpO2.
 
• Invasive hemodynamic monitoring;
 
• Written informed consent.
 
                                     | 
 
• Age less than 18 years old
 
• Terminal hepatic or renal failure just before the procedure
 
• Patient's written refusal to participate in the study
 
 |
| Patients with left ventricular assistive device implantation                                     | 
 
• LVAD implantation
 
• Biventricular heart failure IV
 
• INTERMACS I-III
 
• Hemodynamic support with vasopressors and / or tonics;
 
• Procalcitonin level <math>\geq 0.1</math> ng / ml;
 
• Invasive hemodynamic monitoring;
 
• Written informed consent.
 
 | 
 
• Age less than 18 years old
 
• Acute hepatic or renal failure just before the procedure
 
• Patient's written refusal to participate in the study
 
    |
| Patients in operations with prolonged artificial circulation, hypothermia and circulatory arrest | 
 
• Hemodynamic support with vasopressors and / or tonics;
 
• Bypass duration > 120 minutes
 
• Hypothermia <math>\leq 25</math> 0C
 
• Circulatory arrest
 
   | 
 
• Age less than 18 years old
 
• Terminal hepatic or renal failure just before the procedure
 
• Patient's written refusal to
 
                          |

|  |   |                          |
|--|---|--------------------------|
|  | 
 
• Procalcitonin level <math>\geq 1</math> ng / ml;
 
• Invasive hemodynamic monitoring;
 
• Written informed consent.
 
 | participate in the study |
|--|---|--------------------------|

The study will be conducted in accordance with the international standards Good Clinical Practice, Joint Commission International, scientific ethics (Declaration of Helsinki), as well as the Order of the Minister of Health of the Republic of Kazakhstan dated December 11, 2020 No. 248 "On approval of the rules for conducting clinical trials of drugs and medical devices, clinical laboratory testing of medical devices for diagnostics outside of a living organism (in vitro) and requirements for clinical bases and provision of public services. Issuance of a permit for conducting a clinical trial and (or) testing of pharmacological and medicinal products, medical devices. " The study will also take place in accordance with the recommendations of the Local Ethics Commission at Non-profit JSC «NRCCS». All patients will receive a voluntary informed consent of the established form with permission to use clinical data for scientific purposes. In addition, the research will be strictly monitored by the researchers to ensure that it is free from plagiarism, falsification and fabrication of data in order to achieve the highest ethical conduct of the research. The resulting patient data will be strictly confidential with ensuring privacy through strictly limited access to data, de-identification of data and destruction after the end of the study.

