### Performance evaluation criterias

| Extracorporeal life support system with pulmonary and / or heart failure |
|---|
| Primary results  |

|                          |   |
|--------------------------|---|
| 1                 | Cytokine response [Time: 24-48 hours]

The level of pro- and anti-inflammatory cytokines (IL-1, IL-6, IL-8, IL-10, tumor alpha-factor) before the implantation, 2 hours after the start of ECMO support, explantation of ECMO, 24 hours after explantation of ECMO.     |
| 2                 | SOFA-Score [Time Frame: 24, 48, 72 hours]

Sequential Organ Failure Assessment Score at 24, 48, 72 h (values from 6 to 24, where the higher values explain higher disease severity)   |
| 3                 | Difference of mean arterial pressure [Time Frame: 24, 48, 72 hours]

Comparison of mean arterial pressure at 24, 48, 72 hours between between two interventions (CytoSorb and Jafron)   |
| 4                 | Difference of CVP [Time Frame: 24, 48, 72 hours]

Comparison of CVP at 24, 48, 72 hours between between two interventions (CytoSorb and Jafron)   |
| 5                 | Serum lactate [ Time Frame: 24, 48, 72 hours ]

Level of serum lactate at 24, 48, 72 h  |
| 6                 | 
 
Days on ventilator, vasopressor and renal replacement therapy [ Time Frame: until day 30 post-surgery ]
 

Total days on ventilator, vasopressor and renal replacement therapy within 30 days post-surgery will be assessed |
| 7                 | Doses of vasopressors and / or inotropes ( $\mu\text{g} / \text{h} / \text{kg}$ bodyweight) [Time: first 72 hours]  |
| Secondary results |   |
| 1                 | Inflammatory response - The level of C-reactive protein (CRP) [Time: 24-48 hours]

The level of C-reactive protein (CRP) before the start of ECMO, 2 hours after the implantation of ECMO, during ECMO, 24 hours after ECMO explantation.                        |
| 2                 | Inflammatory response - The level of leukocytes [Time: 24-48 hours]

The level of leukocytes before the start of ECMO, 2 hours after the implantation of ECMO, during ECMO, 24 hours after ECMO explantation.   |

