| 3                 | Inflammatory response - The level of procalcitonin [Time: 24-48 hours]

The level of procalcitonin before the start of ECMO, 2 hours after the implantation of ECMO, during ECMO, 24 hours after ECMO explantation.   |
| 4                 | Level of leukocyte [Time: 24-48 hours]

Level of leukocyte cells in the bloodstream at 24, 48 hours.  |

|                          |  |
|--------------------------|--|
| 5                 | Application and dosage of vasopressors [Deadline: first 48 hours]
Incidence of application and level of dosage of vasopressors on days 2 and 3 after surgery; |
| 6                 | Application and dosage of inotropes [Deadline: first 48 hours]
Incidence of application and level of dosage of inotropes on days 2 and 3 after surgery;       |
| Long-term results |  |
| 1                 | Length of stay in the intensive care unit [Duration: first 48 hours]   |
| 2                 | Length of hospital stay [Term: up to 1 month];   |
| 3                 | 30 day survival rate.  |

| Patients with left ventricular assist device implantation |  |
|--|--|
| Primary results   |  |
| 1   | Difference of Cytokine response [Time: 24-48 hours]
Level of pro- and anti-inflammatory cytokines (IL-1, IL-6, IL-8, IL-10, tumor necrosis factor-alfa, procalcitonin)  |
| 2   | Doses of vasopressors and / or inotropes ( $\mu$ g / h / kg bodyweight)
[Deadline: first 72 hours]  |
| 3   | Renal function [Time: first 72 hours] creatinine level   |
| 4   | Lactate level [Time: first 72 hours]   |
| Secondary results   |  |
| 1   | Inflammatory response - The level of C-reactive protein (CRP) [Time: 24-48 hours]
The level of C-reactive protein (CRP) before the start of the operation, 2 hours after the start of the operation, when the operation is turned off, 24 hours after the shutdown of the operation |
| 2   | Inflammatory response - The level of leukocytes [Time: 24-48 hours]
The level of leukocytes before the start of the operation, 2 hours after the start of the operation, when the operation is turned off, 24 hours after the shutdown of the operation                             |

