| 3   | Inflammatory response - The level of procalcitonin [Time: 24-48 hours]
The level of procalcitonin before the start of the operation, 2 hours after the start of the operation, when the operation is turned off, 24 hours after the shutdown of the operation                       |

|                          |  |
|--------------------------|--|
| 4                 | Application and dosage of vasopressors [Deadline: first 48 hours]
Incidence of application and level of dosage of vasopressors on days 2 and 3 after surgery; |
| 5                 | Application and dosage of inotropes [Deadline: first 48 hours]
Incidence of application and level of dosage of inotropes on days 2 and 3 after surgery;       |
| Long-term results |  |
| 1                 | Length of stay in the intensive care unit [Duration: first 48 hours]   |
| 2                 | Length of hospital stay [Term: up to 1 month];   |
| 3                 | 30 day survival rate.  |

| For operations with prolonged cardio pulmonary bypass, hypothermia and circulatory arrest |  |
|--|--|
| Primary results   |  |
| 1   | Cytokine response [Time: 24-48 hours]
Difference of Cytokine response [Time: 24-48 hours]
Level of pro- and anti-inflammatory cytokines (IL-1, IL-6, IL-8, IL-10, tumor necrosis factor-alfa, procalcitonin, C-reactive protein) |
| 2   | SOFA-Score [Time Frame: 24, 48, 72 hours]
Sequential Organ Failure Assessment Score at 24, 48, 72 h (values from 6 to 24, where the higher values explain higher disease severity)  |
| 3   | Difference of mean arterial pressure [Time Frame: 24, 48, 72 hours]
Comparison of mean arterial pressure at 24, 48, 72 hours between between two interventions (CytoSorb and Jaftron)   |
| 4   | Difference of CVP [Time Frame: 24, 48, 72 hours]
Comparison of mean arterial pressure at 24, 48, 72 hours between between two interventions (CytoSorb and Jaftron)  |
| 5   | Level of Serum lactate [ Time Frame: 24, 48, 72 hours ]
Comparison of mean arterial pressure at 24, 48, 72 hours between between two interventions (CytoSorb and Jaftron)   |
| Secondary results   |  |
| 1   | Inflammatory response - The level of C-reactive protein (CRP) [Time: 24-48 hours]
The level of C-reactive protein (CRP) before the cardiopulmonary bypass 2 hours   |

|                          |  |
|--------------------------|--|

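### For CRP, leukocytes, procalcitonin and ECMO cytokines, the plan names only two-sample tests and no baseline-adjusted model, although pre-treatment samples are scheduled

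*Combined protocol and SAP*

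**What the plan says.** The whole analysis plan is the short section Statistical research. For continuous outcomes it states: "For quantitative data, the nonparametric Mann-Whitney U test and parametric t-test will be performed". Logistic regression is reserved for categorical outcomes, and Cox regression is listed with the survival analyses. No linear, covariate-adjusted or repeated-measures model is named. A list item in the same section, "comparison and analysis of initial data", may mean comparing the arms at baseline, but no model is attached to it.

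The tables under Performance evaluation criterias schedule these pre-treatment samples:

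- **ECMO, primary row 1 (cytokines):** "before the implantation, 2 hours after the start of ECMO support", followed by later samples. This is the only one of the 16 primary rows (7 + 4 + 5) that lists its own pre-treatment time.
- **CRP, leukocytes and procalcitonin, secondary rows in all three tables:** 9 of the 16 secondary rows (6 + 5 + 5). Examples are "The level of C-reactive protein (CRP) before the start of ECMO" and "The level of procalcitonin before the start of ECMO, 2 hours after the implantation of ECMO, during ECMO" for ECMO, and "The level of leukocytes before the start of the operation, 2 hours after the start of the operation" for LVAD.

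Some of these markers are also primary. Procalcitonin is in the LVAD primary cytokine row, and the bypass primary cytokine row includes "tumor necrosis factor-alfa, procalcitonin, C-reactive protein".

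Other outcomes list post-treatment times only, for example "Sequential Organ Failure Assessment Score at 24, 48, 72 h". For SOFA, MAP, CVP, lactate and the LVAD and bypass interleukins, a baseline rests only on the general statement in section 4 that data are gathered before, during and after surgery. Section 4 also makes cytokine measurement depend on the investigators finding a clinical difference between the arms. The ECMO table carries no such condition.

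**The concern.** Two active devices are compared in small groups: per arm, 10 ECMO heart failure, 10 ECMO pulmonary failure, 5 LVAD and 25 prolonged bypass. Precision is scarce. Where a marker is measured before treatment, part of the between-patient spread afterwards can be explained by the starting value. A two-sample test on the post-treatment value leaves that spread in the error term. A two-sample test on change removes it efficiently only when baseline and follow-up are strongly correlated. The plan does not choose between these two, and it does not name the method that does about as well as or better than both over most plausible correlations. What is at stake is wider intervals and lower power, not bias or an inflated error rate.

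**Working it through.** **The plan's own figure.** The only stated figure is 100 participants. It equals the sum of the cells, 2 × (10 + 10 + 5 + 25) = 100. It has no effect size, SD, alpha or power behind it, so there is no power calculation to reproduce.

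**Assumptions, because the documents give none.** Two-sided 5%; normal data (log scale for skewed markers) with SD 1; true difference 0.8 SD; no dropout; baseline-to-follow-up correlation r = 0.3, 0.5 or 0.7, with r of 0.1 or less as the downside. Group sizes n per arm come from section 4.

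**Formulas.** Power is from the noncentral t distribution with noncentrality 0.8 / √(V × 2/n).

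- t-test on the post-treatment value: V = 1, df = 2n − 2.
- t-test on change: V = 2(1 − r), df = 2n − 2. This beats ignoring baseline only if r exceeds 0.5.
- Baseline-adjusted model: V = (1 − r²) × (inflation for chance baseline imbalance, on average 1 + 1/(2n − 4)), df = 2n − 3.

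**Worked case, 25 per arm, r = 0.5.** Unadjusted: 0.8 / √(2/25) = 0.8 / 0.2828 = 2.83 on 48 df, power 79%. Adjusted: V = 0.75 × (1 + 1/46) = 0.766; 0.8 / √(0.766 × 0.08) = 0.8 / 0.2476 = 3.23 on 47 df, power 89%. Change: V = 2 × 0.5 = 1, so 79% again.

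**Power (%) at 0.8 SD, r = 0.3 / 0.5 / 0.7** (adjusted column averaged over chance imbalance)

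| n per arm | t-test, post value | t-test, change | Baseline-adjusted |
|---|---|---|---|
| 25 (bypass) | 79.1 | 64.9 / 79.1 / 94.7 | 81.9 / 88.6 / 97.0 |
| 20 (ECMO, only if combined) | 69.3 | 54.9 / 69.3 / 88.9 | 72.2 / 80.1 / 92.5 |
| 10 (one ECMO subgroup) | 39.5 | 29.9 / 39.5 / 58.9 | 40.5 / 47.4 / 63.1 |
| 5 (LVAD) | 20.0 | 15.5 / 20.0 / 30.2 | 19.1 / 22.2 / 30.3 |

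Simulated trials agree to within about one point, and the adjusted model's null rejection rate is 4.7% to 5.2%.

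**Interval width.** The large-sample ratio √(1 − r²) is 0.954 / 0.866 / 0.714. Allowing for the lost degree of freedom and chance imbalance, the mean interval narrows by about 4/12/28% at 25 per arm, 3/12/28% at 20 and 1/10/26% at 10. At 5 per arm it is about 5% wider at r = 0.3 and about 5% narrower at r = 0.5.

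**Downside.** At r = 0.1, adjusted power is 78.7% against 79.1% (25 per arm), 68.6% against 69.3% (20) and 37.8% against 39.5% (10). At r = 0 it is 78.3%, 68.1% and 37.5%. The loss is about 1 point or less at 20 to 25 per arm, and about 2 points at 10.

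**Two details of the model.**

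- Scale: for a marker with log-SD 1 and a 0.8 SD difference on the log scale, simulated power of a t-test on raw values is 50% at 20 per arm, against 69% on logs.
- Subgroup: if the ECMO subgroups are combined and their means differ by an assumed 0.5/1/1.5 SD, leaving out a subgroup term gives 67/60/50% at 20 per arm, against about 69% with it.

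**The case against.** **The tests might be run on change, which does use baseline.** This is fair, because the plan leaves it open and row titles that speak of a response allow it. A reader might infer that baseline will be ignored. The documents do not say that; they leave its use unspecified. The point survives, because change falls below the unadjusted test at r = 0.3, equals it at r = 0.5, and is still below adjustment at r = 0.7 for 10 to 25 per arm.

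**The cytokine baselines may not exist.** This stands. A reader of the ECMO table alone might take them as already scheduled and paid for, but section 4 makes cytokine measurement conditional. The two places must be reconciled. The point is firm for CRP, leukocytes and procalcitonin, and holds for ECMO cytokines only where the pre-treatment sample is drawn.

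**The correlation is unknown and may be low.** This also stands. Section 3 lists bypass surgery and extracorporeal support as triggers of the inflammatory response, and the baseline is taken before that trigger. Entry at procalcitonin of at least 1 ng/ml (ECMO heart failure and bypass) also narrows the baseline range. It would be too strong to say that adjustment is never worse, since it loses slightly at r of 0.1 or less.

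**The ECMO group may not be 20 per arm.** Section 4 lists heart and pulmonary failure as separate subgroups of 10, and the implementation plan collects them separately, although they share one outcome table. At 10 per arm and r = 0.3 the gain is about 1 point.

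**The named tests are valid.** Agreed. Nothing here shows bias or a false-positive problem. This is a question of efficiency, and nine of the ten rows with a scheduled baseline are secondary.

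**Conclusion.** The point holds as one about precision. The plan names only two-sample tests, does not say which value they use, and names no baseline-adjusted model, although it schedules suitable baselines for CRP, leukocytes and procalcitonin and, subject to the condition in section 4, for ECMO cytokines. In the bypass group, at an assumed 0.8 SD and r = 0.5, adjustment is worth about 10 points of power and an interval about one eighth narrower. The gain is about 3 points at r = 0.3 and 18 at r = 0.7. In separate ECMO subgroups it is about 1, 8 and 24 points. For LVAD there is no useful gain at r = 0.3 to 0.5. All sizes rest on assumed correlations and effects. A reader might take the large-sample narrowing of 5/13/29% as applying here, but at these group sizes it is somewhat too generous. The change should be made because the likely gain is worthwhile and the possible loss is small.

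**What to change.** In Statistical research:

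1. For CRP, leukocytes and procalcitonin in the ECMO and bypass tables, and for ECMO cytokines where the pre-treatment sample is drawn, make the main analysis a linear model of the post-treatment value on device and that marker's baseline. Use the log scale for skewed markers.
2. Name one of the listed post-treatment times for the comparison, or use a repeated-measures model over the listed times.
3. If heart-failure and pulmonary-failure ECMO patients are combined, add a subgroup term. State whether they are.
4. Keep a rank-based analysis as a sensitivity check, for example ranked outcome adjusted for ranked baseline.
5. Extend the model to SOFA, MAP, CVP, lactate and the bypass interleukins only where a pre-treatment value is recorded.
6. For LVAD, report estimates with confidence intervals.
7. Reconcile the conditional cytokine measurement in section 4 with the ECMO table.

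The cost is revised wording and a little more analysis work. No extra patients are needed, and no extra samples for CRP, leukocytes or procalcitonin. For cytokines, whether extra samples are needed depends on how item 7 is settled.

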#### **4. Research methods and ethical issues.**

All patients admitted to Non-profit JSC “NRCCS” who meet the study criteria (patients on an extracorporeal life support system, mechanical circulatory support, surgery on the aortic arch) will be included in the study after obtaining a signed informed consent. Participants will be randomized into 2 groups in a 1: 1 division.

**Intervention team # 1** using an extracorporeal hemoperfusion device Jaftron (Zhuhai Jaftron Biomedical, China) (50 patients) in subgroups: A (n = 10) - patients on extracorporeal life support systems with heart failure; B (n = 10) - patients on extracorporeal life support systems with pulmonary failure; C (n = 5) - patients with implantation of a left ventricular accessory device; D (n = 25) - during operations with prolonged artificial circulation, hypothermia and circulatory arrest.

**Intervention team # 2** using extracorporeal cytokine, CytoSorb (CytoSorbents Corporation, Monmouth Junction, NJ, USA) (50 patients) in subgroups: A (n = 10) - patients on extracorporeal life support systems in heart failure; B (n = 10) - patients on extracorporeal life support systems with pulmonary failure; C (n = 5) - patients with implantation of a left ventricular accessory device; D (n = 25) - during operations with prolonged artificial circulation, hypothermia and circulatory arrest.

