#### **Study design.**

Study type: interventional (clinical study)

Set of participants: 100 participants

Distribution: randomized

Interventional model: parallel

Masking: no

Primary Goal: Treatment

| Intervention team (1 group)  | Intervention / treatment (device)  |
|--|--|
| Extracorporeal hemoperfusion device will be installed in the device of the extracorporeal life support system for heart failure...
(10 patients)        | HA330 - Jafron Biomedical Co., Ltd., China
- extracorporeal hemocorrection, which is based on the removal of cytokines from whole blood by sorption on a special hemoabsorbent due to the peculiarities of its porous structure and inner surface, which is indicated in conditions where cytokine levels are extremely elevated. |
| Extracorporeal hemoperfusion device will be installed in the device of the extracorporeal life support system for pulmonary failure
(10 patients).      | HA330 - Jafron Biomedical Co., Ltd., China
- extracorporeal hemocorrection, which is based on the removal of cytokines from whole blood by sorption on a special hemoabsorbent due to the peculiarities of its porous structure and inner surface, which is indicated in conditions where cytokine levels are extremely elevated. |
| An extracorporeal hemoperfusion device will be installed in patients before / during the implantation of a left ventricular assist device
(5 patients). | HA330 - Jafron Biomedical Co., Ltd., China
- extracorporeal hemocorrection, which is based on the removal of cytokines from whole blood by sorption on a special hemoabsorbent due to the peculiarities of its porous structure and inner surface, which is indicated in conditions where cytokine levels are extremely elevated. |
| An extracorporeal hemoperfusion device will  | HA330 - Jafron Biomedical Co., Ltd., China   |

|   |  |
|---|--|
| be installed in patients during operations with prolonged cardiopulmonary bypass, hypothermia and circulatory arrest. (25 patients).  | - extracorporeal hemocorrection, which is based on the removal of cytokines from whole blood by sorption on a special hemoadsorbent due to the peculiarities of its porous structure and inner surface, which is indicated in conditions where cytokine levels are extremely elevated. |
| Intervention team (2 groups)   |  |

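### Two competing tests are planned for each outcome type, neither is named as decisive, and no alpha or sidedness is stated

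*Combined protocol and SAP*

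**What the plan says.** The analysis plan is one short paragraph under Statistical research.

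- Quantitative outcomes: the "nonparametric Mann-Whitney U test and parametric t-test will be performed".
- Categorical outcomes: "for qualitative studies, the nonparametric Fisher's exact test and the parametric" chi-square test.
- Further methods: "Also, logistic regression for categorical outcomes and survival analyzes" by Kaplan-Meier and Cox regression.
- Software: "statistical analysis will be performed using SPSS Statistics version 22".

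The paragraph gives no condition for using one member of a pair over the other, such as a distributional check or an expected cell count. It names no primary test, alpha or sidedness, and the rest of the available text does not supply them.

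Most primary results in the Performance evaluation criterias tables are quantitative. In the extracorporeal life support (ECLS) table the first is "The level of pro- and anti-inflammatory cytokines". SOFA, arterial and venous pressure, lactate, days of support and drug doses follow. The design is "Set of participants: 100 participants", unmasked. Section 4 adds that "Participants will be randomized into 2 groups in a 1: 1 division", with subgroups of 10, 10, 5 and 25 per arm.

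**The concern.** Read literally, every quantitative outcome yields two p-values, and nothing says which one is the result. Read as a list of methods to choose from, the choice is still unmade when the unmasked data are examined. Either way the analyst can pick.

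The pick matters because the tests answer different questions. On the raw scale the t-test compares means and Mann-Whitney compares ranks. For skewed laboratory markers they will sometimes disagree. The programme plan uses the results to settle on an effective treatment method and to write practice protocols, so conflicting verdicts with no rule to resolve them would be a real problem.

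**Working it through.** **The plan's own figures.** There is no alpha, power, effect size or SD to reproduce. The arithmetic of the sample size does check: 10 + 10 + 5 + 25 = 50 per arm, and 2 × 50 = 100. The outcome tables correspond to 20 per arm (ECLS, 10 + 10), 5 per arm (LVAD) and 25 per arm (prolonged bypass).

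**Assumptions.** Two-sided 5% per test. Outcome distributions are not given, so a range was used: normal, lognormal with log SD 0.5, 1.0 and 1.5, and t with 3 df. Binary event rates are also not given; 10% to 50% was covered.

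**Quantitative outcomes.** The quantity is the null probability that at least one test is significant: P(either) = P(t) + P(MW) − P(both). Each cell rests on 100,000 simulated null trials (Monte Carlo SE about 0.08 points). The t-test is pooled-variance, and Mann-Whitney is exact at 5 per arm.

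| Per arm | Distribution | t-test | Mann-Whitney | Both | Either |
|---|---|---|---|---|---|
| 20 | normal | 5.12% | 4.91% | 3.99% | 6.04% |
| 20 | lognormal, log SD 1 | 3.92% | 4.89% | 2.30% | 6.52% |
| 25 | normal | 4.91% | 4.90% | 3.91% | 5.90% |
| 25 | lognormal, log SD 1 | 3.91% | 4.80% | 2.16% | 6.56% |
| 5 | normal | 4.99% | 3.10% | 2.91% | 5.18% |
| 5 | lognormal, log SD 1 | 3.08% | 3.17% | 1.91% | 4.34% |

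- For example, 25 per arm, lognormal: 3.91 + 4.80 − 2.16 = 6.55, which is 6.56 before rounding.
- Across all five distributions, the either-test rate is 6.0% to 6.5% at 20 per arm and 5.9% to 6.6% at 25.
- At 5 per arm it is 4.1% to 5.2% with exact Mann-Whitney (6.0% to 6.3% with the asymptotic version, another choice left open).
- Requiring both tests to be significant would be conservative, as the Both column shows.
- Two independent tests would give 1 − 0.95² = 9.75%. That does not apply here, because the tests are strongly correlated.

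**Binary outcomes.** All 2×2 tables were enumerated at 5, 10, 20, 25 and 50 per arm. No table is significant by Fisher but not by uncorrected chi-square. So P(either) equals P(chi-square) exactly.

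| Per arm | Event rate | Fisher | Chi-square | Either |
|---|---|---|---|---|
| 25 | 26% | 2.2% | 5.4% | 5.4% |
| 25 | 40% | 3.0% | 6.0% | 6.0% |
| 20 | 26% | 2.4% | 5.2% | 5.2% |
| 20 | 40% | 2.4% | 4.8% | 4.8% |

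Any excess over 5% is the chi-square approximation itself. The ratio of the two error rates at 25 per arm is 5.4/2.2 = 2.5 and 6.0/3.0 = 2.0.

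**What a single better analysis gains.** Take 20 per arm and assume a log-scale difference of 0.7, log SD 1 and a baseline correlation of 0.5. In 20,000 simulated trials, power was about 70% for regression of the log value on arm and log baseline, 56% for Mann-Whitney and 41% for the raw t-test. Under the null the regression held 5.0%. With that effect, Mann-Whitney and the raw t-test disagreed on significance in 22% of trials.

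**The case against.** The strongest reply is that the paragraph labels each pair as nonparametric and parametric, and so can be read as a list of methods to be matched to the data. On that reading nobody intends to report the smaller p-value, and the inflation is hypothetical. This stands in part. The documents do not state a rule that either test may count, so the error rates above are conditional on one. The missing selection rule remains on both readings.

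Three stronger inferences are tempting, and the documents do not support them:

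- **That the false-positive rate exceeds 5% for every outcome.** The plan sets no 5% level, the excess needs an either-test rule, and in the LVAD table with exact Mann-Whitney it all but vanishes.
- **That running Fisher beside chi-square inflates the error.** It cannot, since every Fisher-significant table checked is also chi-square-significant. Comparing chi-square with Fisher's 2% to 3% mistakes Fisher's conservatism for inflation.
- **That the either-test rate is about 7%, as simulated for skewed data at 50 per arm.** No outcome table has 50 per arm, and the plan describes no pooled analysis.

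It is also fair to say that 1 to 2 points is small. The primary rows number 7, 4 and 5 in the three tables. At one unadjusted 5% test each, they would give 1 − 0.95⁷ = 30%, 1 − 0.95⁴ = 19% and 1 − 0.95⁵ = 23% if independent. That is the larger problem. But a multiplicity adjustment would not say which of two p-values enters it, so this point needs its own repair.

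**Conclusion.** The point holds as an unresolved choice of analysis. The plan names no decisive test for either outcome type and states no alpha or sidedness, in an unmasked trial.

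For quantitative outcomes, taking the better of the two tests at an assumed two-sided 5% gives about 6% to 7% per comparison at 20 to 25 per arm (normal to lognormal with log SD 1), and essentially no inflation at 5 per arm with exact Mann-Whitney. For binary outcomes the pairing adds no error. What is open is a choice between tests whose error rates differ about twofold at 25 per arm (2.2% to 3.0% against 5.4% to 6.0%, at assumed event rates of 26% to 40%).

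The inflation is modest. The stronger reasons to act are conflicting verdicts on skewed markers and the precision lost by ignoring baseline values. The change should be made before any comparison by arm is examined.

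**What to change.** In Statistical research, state alpha and sidedness and name one primary analysis per outcome type:

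- **Positive, skewed markers with a pre-procedure sample (cytokines, CRP, procalcitonin):** linear regression of the log value on arm and log baseline. In the ECLS table add the heart-failure or pulmonary-failure subgroup. The LVAD and bypass tables are single subgroups and need no such term. Use all four subgroups only if the populations are pooled.
- **SOFA, mean arterial pressure and CVP:** the same model untransformed, with baseline where it is measured.
- **Outcomes that can be zero (drug doses, days of support):** Mann-Whitney, since the log is undefined at zero. State whether it is exact or asymptotic.
- **Binary outcomes:** one named test, for example Fisher's exact.

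Assign the remaining quantitative outcomes (lactate, creatinine, leukocytes, lengths of stay) to one of these classes in the same text. Report the other planned tests as labelled sensitivity analyses.

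The cost is a short paragraph or table in the analysis section. No patients or procedures are added. The adjusted models use pre-procedure values that the ECLS cytokine row and the CRP and procalcitonin rows already list. For cytokines in the LVAD and bypass tables, confirm that the pre-procedure sample described in section 4 is taken.
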